2.4 Determination of sample size

The sample size of 15 subjects in Dose Arms 1 and 2, is mainly based on the efficacy objective of the study. In addition, the inclusion of 15 subjects in Dose Arms 1 and 2 will ensure that sufficient data are available to form conclusions about the safety of administering UCB7665. Based on the safety data from Dose Arms 1 and 2, the sample size of 6 to 12 subjects in Dose Arms 3, 4 and 5 were judged to be sufficient in order to explore subjects' safety and IgG reductions under different dose regimens and is not based on a formal sample size calculation.

For Dose Arms 1 and 2 an approximate sample size calculation for the efficacy variable "maximum increase from Baseline in platelet count" shows that 15 subjects would be sufficient to show a change from Baseline with 1-sided testing at 5% and power of 80%. The anticipated change is based on an assumed Baseline average of $25 \times 10^9/L$ and a clinically meaningful maximum value of $100 \times 10^9/L$. The calculation made use of platelet count data presented in a publication by Robak (Robak et al, 2009), but it is approximate as maximum changes from Baseline for individual subjects were not available, necessitating the use of the maximum average platelet count instead. The standard deviation (SD) is taken from visual inspection.

With 15 subjects, the responder endpoints will confirm a true 50% response rate, in excess of the maximum 15% anticipated with no treatment benefit, with power in excess of 80%.

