3 DATA ANALYSIS CONSIDERATIONS

3.1 General presentation of summaries and analyses

Statistical evaluation will be performed by PAREXEL. The datasets will follow the UCB analysis data model (ADaM) specifications.

All analyses will be performed using SAS version 9.3 or higher (SAS Institute, Cary, North Carolina, United States of America). Continuous variables will be summarized by visit (where applicable) including number of subjects (n), arithmetic mean, SD, median, minimum and maximum. Categorical variables will be summarized by visit (where applicable) with frequency counts and percentages with 95% confidence intervals (CI) where stated. Geometric coefficient of variation (geoCV), geometric mean (geoMean) and 95% CI for the geoMean will also be presented in the descriptive statistics for the PK concentration data.

When reporting relative frequencies or other percentage values, the following rules apply:

- For values where all subjects fulfill certain criteria, the percentage value will be displayed as 100
- For values where the absolute frequency is zero, there will be no percentage displayed at all
- All other percentage displays will use 1 decimal place

Percentages displayed based on continuous data (eg, percentage changes from baseline) will be displayed to 1 decimal place.

When reporting descriptive statistics, the following rules will apply in general:

- n will be an integer
- Mean (arithmetic and geometric), SD and median will use 1 decimal place more than the original data
- Minimum and maximum will be reported using the same number of decimal places as the original value
- If no subjects have data at a given timepoint, for example, then only n=0 will be presented. If n<3, present the n, minimum and maximum only. If n=3, present the n, mean, median, minimum and maximum only. The other descriptive statistics will be left blank.

When reporting descriptive statistics for PK data, the following rules will apply with regard to rounding and precision:

- Individual values for PK concentration data will be reported to the same level of precision as received from the bioanalytical laboratory
- Descriptive statistics for PK concentration data will be reported to the same level of precision as the individual data for the minimum and maximum, and to 1 additional significant figure for the mean (arithmetic and geometric), median, SD and 95% CI for the geoMean
- Geometric CV will be reported as a percentage to 1 decimal place

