8.1.1 Definition of variables

The main efficacy variable is defined as the following:

- **Maximum Increase from Baseline:** the Maximum Increase from Baseline (Day 1, predose) is defined as the highest positive change from Baseline during the study. In the event that the platelet count was to decrease during the study the Maximum Increase from Baseline may be negative and would correspond to the smallest decrease from the Baseline value

The following additional variables will be defined for the platelet count, the calculation rules for which are provided in the section immediately below:

- **Response:** a platelet count $\geq 30 \times 10^9/L$ and at least 2-fold increase from the Baseline value, by visit, and at any timepoint during the study
- **Time to Response:** the first time that a given response is achieved during the study. Thus, in the event that the platelet count was to increase above the threshold level, decrease below the threshold level, and subsequently increase again the time to response would be to the first time the definition of response was achieved. The time to response will be calculated in days and presented to 1 decimal place in the listings.

Time to response (days) = Date/time of first response – Date/time of first dose of UCB7665

- **‘No’ or ‘Loss of’ Response:** a platelet count $< 30 \times 10^9/L$ OR $\geq 30 \times 10^9/L$ WITHOUT at least a 2-fold increase from the Baseline value, by visit
- **Duration of Response (including Complete Response, Response and Platelet Count $\geq 50 \times 10^9/L$):** the duration of the first time the response was achieved to first loss of response. The duration of response will be calculated in days and presented to 1 decimal place in the listings.

Duration of response (days) = Date/time of loss of first response – Date/time of first response, where “loss of first response” is defined as platelet count $< 30 \times 10^9/L$ OR (platelet count $\geq 30 \times 10^9/L$ WITHOUT at least a 2-fold increase from the Baseline value)

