 - A minimum of 10 out of 14 measurements must be available for the calculation in Dose Arm 1; a minimum of 9 out of 12 measurements must be available for the calculation in Dose Arm 2; a minimum of 8 out of 11 must be available for the calculation in Dose Arm 3; a minimum of 7 out of 9 must be available for the calculation in Dose Arms 4 and 5. These include the Baseline and measurement at the last visit
 - The AUEC will not be calculated in the case of early withdrawal from the study

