10.3 Clinical laboratory evaluations

Laboratory data (chemistry [excluding follicle stimulating hormone, FSH], hematology, coagulation and urinalysis) and changes from Baseline (if applicable) for numeric variables will

be listed by dose arm and visit. Any laboratory measurements that are BLQ or ALQ will be handled as described in Section 4.2.2. Values outside the reference range for the numeric variables will be flagged in the listings and in addition, results considered as markedly abnormal laboratory results (CTCAE Grade 3 and above) will be listed separately. The reference ranges will also be reported in the listings.

Chemistry [excluding FSH], hematology and coagulation variables will be summarized by dose arm at each visit, for both absolute values and changes from Baseline.

Laboratory variables will be grouped according to the laboratory function panel (Table 10-1) and categorized as normal, high or low, if applicable, based on the reference range supplied by the analytical laboratory. For selected variables that are identified in Table 10-1, the change in category from Baseline will be presented in shift tables at all post-Baseline visits.

Table 10–1: Clinical laboratory measurements

Category	Panel	Variable
Serology	Serology	HIV, HBsAg, anti-HBs, anti-HBc, anti-HCV
Hematology	Red blood cell	RBC count ^a , hemoglobin ^a , hematocrit
	Platelet	Platelet ^{ab}
	White blood cell	WBC count ^a
	White blood cell differential	Absolute counts: ANC ^a , basophils ^a , eosinophils ^a , ALC ^a , monocytes ^a Percentages: neutrophils/leukocytes ^a , basophils/leukocytes ^a , eosinophils/leukocytes ^a , lymphocytes/leukocytes ^a , monocytes/leukocytes ^a .
Coagulation	Coagulation	INR ^a , prothrombin time ^a , aPTT ^a , fibrinogen ^a
Chemistry	Electrolytes	Sodium ^a , chloride ^a , potassium ^a
	Minerals	Calcium ^a , phosphate ^a , magnesium ^a
	Kidney function	BUN ^a , creatinine ^a
	Proteins	Total protein ^a , albumin ^a , α1-globulin ^a , α2-globulin ^a , β-globulin ^a , gamma globulin ^a . For all parameters except total protein, both absolute and percentage values will be reported as part of the serum protein electrophoresis.
	Liver function	AST ^a , ALT ^a , GGT ^a , ALP ^a , LDH ^a , total bilirubin ^a , direct bilirubin (if indicated)
	Lipids	Total cholesterol ^a , triglycerides ^a
	Hormones	FSH
	Other	hsCRP ^a , amylase ^a
Urinalysis	Dipstick	pH ^a , protein, glucose, ketones, urobilinogen, bilirubin, blood, nitrite, leucocytes

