Category	Panel	Variable
	Quantitative	Albumin, creatinine
	Urine sediment ^c	RBC, WBC, epithelial cells, casts, crystals, yeast, bacteria, amorphous urates, amorphous phosphates
Pregnancy test		Urine HCG ^d , serum HCG ^e
Other		HbA1c

ALC=absolute lymphocyte count; ALP=alkaline phosphatase; ALT=alanine aminotransferase; ANC=absolute neutrophil count; anti-HBc=hepatitis B core antibody; anti-HBs=hepatitis B surface antibody; anti-HCV=hepatitis C virus antibody; aPTT=activated partial thromboplastin time; AST=aspartate aminotransferase; BUN=blood urea nitrogen; FSH=follicle stimulating hormone; GGT=gamma-glutamyltransferase; HbA1c=glycosylated hemoglobin; HBsAg=hepatitis B surface antigen; HCG=human chorionic gonadotropin; HIV=human immunodeficiency virus; hsCRP=high sensitivity C-reactive protein; INR=International Normalized Ratio; LDH=lactate dehydrogenase; RBC=red blood cell; TB=tuberculosis; WBC=white blood cell.

^a Shift tables will be presented for these variables.

^b Only platelet results measured at the local laboratory will be included in the safety outputs. Measurements obtained at the central laboratory will be reported as part of the efficacy analyses.

^c If indicated, based on results of urine dipstick.

^d Urine pregnancy test will be performed predose on dosing days and at the End-of-Study Visit

^e Serum pregnancy test is done at Visit 1 (Screening) and to confirm results of positive urine test if applicable.

The number and percentage of subjects with markedly abnormal laboratory results (CTCAE Grade 3 and above) will be tabulated by dose arm and laboratory variable at each visit. The criteria for identifying abnormal laboratory results are detailed in [Section 13.5](#).

Figures of mean and mean change from Baseline will be plotted over time by dose arm for all quantitative laboratory variables (with the exception of any variables measured only at Screening and/or Baseline, eg serology, HbA1c and FSH), with all dose arms overlaid on the same plot. The reference range for each variable (male and female, if applicable) will be included on the plot for absolute values. For the differential WBC counts, figures will be presented based on percentage values only.

Any additional laboratory variables not included in the outputs described previously (including pregnancy testing, FSH and serology) will be listed separately.

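### The platelet shift table uses the laboratory's normal/high/low range, so a subject already low at Baseline, as nearly all ITP subjects will be, cannot be recorded as falling

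*SAP*

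**What the plan says.** SAP Section 10.3 groups laboratory variables by panel and has them "categorized as normal, high or low, if applicable, based on the reference range supplied by the analytical laboratory". For the variables marked in Table 10-1, "the change in category from Baseline will be presented in shift tables at all post-Baseline visits".

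The platelet row of Table 10-1 carries footnotes a and b. Footnote a reads "Shift tables will be presented for these variables". Footnote b reads "Only platelet results measured at the local laboratory will be included in the safety outputs". The words 'if applicable' in Section 10.3 therefore do not exempt platelets, and Section 10.3 sets no other categories for them.

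The study population has persistent or chronic primary ITP (Section 2.3). On the expected starting level, Section 2.4 says "The anticipated change is based on an assumed Baseline average of" 25 x10^9/L.

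**The concern.** A shift table counts how many subjects changed category, and in which direction. That only works if subjects start in a category with room on both sides. In thrombocytopenia nearly everyone starts in the lowest of the three categories, so the platelet table has a row for them but no cell for worsening.

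A count that collapses, a count that does not move and a moderate rise all land in the low-to-low cell. The table would be produced at every post-Baseline visit, in a study whose primary objective is safety, for the laboratory variable that defines the disease. Someone reading a full low-to-low cell could take it as stability.

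**Working it through.** The plan states no figure for this table, so there is none to reproduce. The check has two parts: the logic of the cells, and a rough size.

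**Logic.** Take an assumed reference range of 150 to 400 x10^9/L.

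- 25 to 12.5, 25 to 5 and 80 to 10 all give low to low.
- 25 to 60 also gives low to low, as it would for any lower limit above 60. That rise is 60/25 = 2.4-fold and ends above 30, so it meets the Section 8.1.1 Response rule (at least 30 x10^9/L "and at least 2-fold increase from the Baseline value, by visit, and at any timepoint during the study").
- 25 to 100, a Complete Response, gives low to low.
- 25 to 160 gives low to normal. A count above 400 would give low to high.

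**Inputs for the size.** From the SAP: mean Baseline 25 (Section 2.4) and cut-points 30, 50 and 100 (Section 8.1.1). Assumed, because the SAP does not give them: lower reference limit 100 to 150; lognormal true level with SD 8, 12.5 or 20; lognormal within-subject error with CV 10%, 20% or 30%.

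**Share low on measured Baseline.** The log-variance is v = ln(1 + (SD/25)²) + ln(1 + CV²), the log-mean is ln 25 − v/2, and the share low is Φ[(ln L − log-mean)/√v] for lower limit L. The least favourable case is SD 20, CV 30%, L = 100:

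- v = ln 1.64 + ln 1.09 = 0.4947 + 0.0862 = 0.5809, so √v = 0.762
- log-mean = 3.2189 − 0.2904 = 2.9284
- z = (4.6052 − 2.9284)/0.762 = 2.20, so the share low is 98.6%

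Across the other scenarios the share rises to 100%. As a wider check on the true level only, with SD up to 50, it is 95.8% to 100%.

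**Movement at one visit.** 400,000 simulated subjects per scenario; ranges are over the nine SD-by-CV combinations.

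| Categories | Down if every true count halves | Up if halved | Down if no true change |
|---|---|---|---|
| Reference limit 100 | 0.0–1.3% | | |
| Reference limit 150 | 0.0–0.3% | | |
| Bands 30/50/100 | 23.4–26.7% | | 4.1–14.5% |
| Bands 10/30/50/100 | 53.2–63.1% | 0.0–0.8% | 6.0–17.5% (up 6.0–17.4%) |
| Bands 10/20/30/50/100 | 67.0–93.4% | 0.0–1.4% | 9.3–28.0% (up 9.3–28.0%) |

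Per 15 subjects with counts halved, the reference-range table moves at most 15 x 1.3% = 0.2 down. Bands 10/30/50/100 move 15 x 53.2% = 8.0 to 15 x 63.1% = 9.5 down. With no true change those bands move 15 x 6.0% = 0.9 to 15 x 17.5% = 2.6 each way.

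With a lower limit of 100, the 10/30/50/100 bands are low subdivided with normal on top. With a limit of 150, keeping normal adds one more cut; in the halved case it can add no more downward movers than cross 150, which is 0.0–0.3%.

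**Lowest value instead of each visit.** For the number of counts, Section 8.1.1 says "A minimum of 10 out of 14 measurements must be available for the calculation in Dose Arm 1", and gives 9 measurements in all for Dose Arms 4 and 5. Removing Baseline leaves 14 − 1 = 13 and 9 − 1 = 8. This is the central-laboratory schedule, assumed here to apply locally too. With bands 10/30/50/100 and no true change, the lowest value falls a band in 13.9–41.1% of subjects with 8 counts and 15.5–46.2% with 13.

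**The case against.** The strongest reply is that platelet falls are already reported for the same data. Section 10.3 summarises hematology by visit as values and changes from Baseline, and Section 3.1 says "Continuous variables will be summarized by visit (where applicable) including number of subjects (n), arithmetic mean, SD, median, minimum and maximum". The minimum change is therefore the largest fall in each arm at each visit. Listings give changes and flag out-of-range values, mean-change figures are planned, and with 6 to 15 subjects per arm individual falls can be read directly. The rise from 25 to 60 is captured by the responder tables in Section 8.1.3.3.

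This stands, and it keeps the point small. A reader might infer that the safety report hides platelet falls; the SAP does not support that. Nor can the table be said never to show a fall: a subject who starts normal could drop to low, which is where the 0.0–1.3% comes from. It also shows rises into high, not only into normal. Nothing is inferred here about the markedly abnormal criteria in Section 13.5, because its current table was not available to check.

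What the reply does not do is make the platelet shift table informative. Means and minima do not count how many subjects worsened. The central-count summaries are not a full substitute, since they use the Full Analysis Set and stop at rescue medication (Sections 3.5.3 and 8.1); Section 10.3 states no such cut for local counts.

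It is also fair that the reference limit, SD, CV and the halving scenario are outside the SAP, and that 25 is a planning mean. The structural point needs only that nearly all subjects start low.

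**Conclusion.** The point holds as a minor defect confined to one table. For a subject low at Baseline, the planned platelet shift table has no cell for worsening, and under the stated assumptions 98.6% to 100% of subjects start there. A halving of every count would register as a downward shift in at most 1.3% of subjects at a visit, against 53% to 63% with low subdivided at 10, 30, 50 and 100. Those percentages rest on the assumed reference limit, spread and fluctuation; the direction of the conclusion does not. The primary safety variable, occurrence of TEAEs, is unaffected, and other planned outputs still show falls.

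**What to change.** In Section 10.3 and Table 10-1, for platelets only, subdivide the low category by count. Use the SAP's own 30, 50 and 100 x10^9/L, plus at least one lower cut-point within the Baseline range (10, or 10 and 20, at the sponsor's choice). The lower cut-point matters: without it only 23% to 27% move down when counts halve. Keep the normal and high categories. A single top band of 100 and above would merge normal with high counts and lose sight of an overshoot.

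Keep the shift from Baseline to each scheduled post-Baseline visit, by dose arm on the Safety Set, and read upward and downward shifts together. Do not make Baseline-to-lowest-value the main table: it drops bands often from fluctuation alone, and more often in arms with more visits. If one is added, label it descriptive with that caveat.

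The cost is one sentence in the SAP and one reprogrammed table on data already collected. The downsides are a platelet-specific shell outside the generic laboratory layout, and about 6% to 17.5% of subjects changing band each way per visit by fluctuation alone with cut-points 10/30/50/100 (9.3% to 28.0% if 20 is added).

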10.4 Vital signs, physical findings, and other observations related to safety

10.4.1 Vital signs

The following vital signs measurements will be obtained:

- Pulse rate
- Systolic and diastolic blood pressure
- Temperature
- Respiratory rate

A by-subject listing of all vital sign measurements and change from Baseline will be presented by dose arm and timepoint. The listing will include a flag for measurements identified as treatment-emergent markedly abnormal (TEMA)/potentially clinically significant (PCS) as calculated by the criteria outlined in [Table 10-2](#).

Descriptive statistics will be reported for all vital sign measurements. Measured values and changes from Baseline will be summarized by vital signs variable and timepoint for each dose arm.

Figures of mean change from Baseline will be presented for each variable by dose arm. All dose arms will be overlaid on the same plot.

The number and percentage of subjects with TEMA/PCS vital sign values will be summarized by dose arm at each timepoint.

Table 10-2: TEMA/PCS criteria for vital signs

Variable	Unit	Low	High
Systolic blood pressure	mmHg	Value < 90 and ≥ 20 decrease from Baseline	Value > 180 and ≥ 15 increase from baseline
Diastolic blood pressure	mmHg	Value < 50 and ≥ 15 decrease from Baseline	Value > 105 and ≥ 15 increase from Baseline

Note: The change in measurement (increase or decrease) will be calculated relative to the value obtained at Baseline.

^aBoth conditions must be satisfied for a measurement to be considered PCS.

Repeated and unscheduled measurements will be handled as described in [Section 4.3](#).

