- QT corrected for heart rate using Fridericia’s formula ($QTcF = QT/RR^{0.33}$)

The individual measurements and the mean of the triplicate measurements will be reported in the by-subject listings. The listing will also include the change from Baseline and percentage change from Baseline (based on the mean of the triplicate measurements at each timepoint). TEMA/PCS ECG values will be flagged in the listing.

Change #22

Electrocardiograms (Section 10.4.2)

The following table has been added:

Variable	Criteria
QT corrected for heart rate using Fridericia’s formula (QTcF)	≥501ms OR ≥60ms compared to baseline
PR prolongation	≥210ms and ≥10ms change from baseline

Change #23

Classification of markedly abnormal laboratory values based in CTCAE grades (Section 13.5)

Table 13-2 has been updated as follows:

Category	Panel	Variable	Criteria (CTCAE ^a Grade 3 and above)
Hematology	Red blood cell	Hemoglobin (Decrease)	<8g/dL (<80g/L)

Category	Panel	Variable	Criteria (CTCAE ^a Grade 3 and above)
		Hemoglobin (Increase)	>4g/dL (>40g/L) above ULN OR >4g/dL (>40g/L) above baseline if baseline is > ULN
	White blood cell	WBC count (Decrease)	<2000/mm ³ (<2.0x10 ⁹ /L)
		WBC count (Increase)	>20,000/mm ³
	White blood cell differential	ALC (Decrease)	<500/mm ³ (<0.5x10 ⁹ /L)
		ALC (Increase)	>20,000/mm ³ (>20x10 ⁹ /L)
		ANC	<1000/mm ³ (<1.0x10 ⁹ /L)
Chemistry	Liver Function	ALT	≥5.0xULN
		ALP	>5.0xULN
		AST	>5.0xULN
		Total bilirubin	>3.0xULN
		GGT	>5.0xULN
	Kidney Function	Creatinine	>3.0xbaseline value OR >3.0xULN
		Creatinine (Acute kidney injury)	>3xbaseline value OR >4xULN
		Creatinine phosphokinase	>5xULN
		eGFR or CrCl	≤29ml/min/1.73m ²
	Minerals	Calcium (Decrease)	corrected <7mg/dL (<1.75mmol/L); ionized <0.9 mmol/L
		Calcium (Increase)	corrected >13.5mg/dL (>3.1mmol/L); ionized >1.8mmol/L
		Magnesium (Decrease)	<0.4mmol/L (<0.9mg/dL)
		Magnesium (Increase)	>1.23mmol/L (>3mg/dL)
		Phosphate	<0.6mmol/L (<2mg/dL)
	Metabolic	Glucose (Decrease)	<2.2mmol/L (<40mg/dl)

Category	Panel	Variable	Criteria (CTCAE ^a Grade 3 and above)
		Glucose (Increase)	>250mmol/L (>13.9mg/dl)
	Electrolytes	Potassium (Decrease)	<3.0mmol/L
		Potassium (Increase)	>6.0mmol/L
		Sodium (Decrease)	<130mmol/L
		Sodium (Increase)	>155mmol/L
	Lipids	Total cholesterol	>10.34mmol/L (>400mg/dL)
		Triglycerides	>5.7mmol/L (>500mg/dL)
	Proteins	Albumin	<20g/L (<2g/dL)
	Other	Amylase	>2.0xULN

14.3 Amendment 3

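### The Grade 3+ laboratory table is not tied to Baseline status, so the planned summaries cannot separate new from persisting marked abnormalities

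*SAP*

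**What the plan says.** Section 10.3 plans three displays that bear on this point.

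- A listing: "results considered as markedly abnormal laboratory results (CTCAE Grade 3 and above) will be listed separately".
- A summary table: "The number and percentage of subjects with markedly abnormal laboratory results (CTCAE Grade 3 and above) will be tabulated by dose arm". In full, the counts "will be tabulated by dose arm and laboratory variable at each visit". For the cut-offs it refers to Section 13.5: "The criteria for identifying abnormal laboratory results are detailed in" that section.
- Shift tables for selected variables, in which "the change in category from Baseline will be presented in shift tables at all post-Baseline visits". The categories are fixed just before: variables are "categorized as normal, high or low, if applicable, based on the reference range supplied by the analytical laboratory".

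Section 10.3 sets no condition on the subject's Baseline grade for the Grade 3+ table.

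Other safety sections do set one. Section 10.4.1 provides a flag for "measurements identified as treatment-emergent markedly abnormal (TEMA)/potentially clinically significant (PCS") and, in Table 10-2, requires both an absolute limit and a change from Baseline for blood pressure. Table 10-3 in Section 10.4.2 does the same for PR. Section 10.2 counts an event already present before the first infusion as a TEAE only if it worsens. Section 9.3.4 requires a fold increase before a Baseline-positive subject counts as treatment-emergent for anti-drug antibodies.

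**The concern.** The study is open-label and every arm receives UCB7665, so there is no control group against which to read a laboratory abnormality. The subject's own Baseline is the main reference. A summary of marked abnormalities that ignores Baseline counts a subject who was Grade 3 or above before the first infusion, and stays so, at every later visit. That subject looks the same in the table as one whose value became Grade 3 after dosing.

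Safety and tolerability are the primary objective, and laboratory values are named among the other safety variables in Section 2.2.1.2. With 6 to 15 subjects per arm, one persisting case shifts the displayed percentage noticeably. What is at stake is how one safety table is read, not a test or a decision rule.

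**Working it through.** The plan gives no figure to reproduce here. The check compares the rules and then works out the weight of one subject.

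**Step 1. Rules side by side**

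| Output | Absolute limit | Link to Baseline |
|---|---|---|
| Grade 3+ laboratory table (10.3) | Yes | None stated in 10.3 |
| Blood pressure (Table 10-2) | Yes | Change from Baseline also required |
| PR (Table 10-3) | 210 ms or more | Change of 10 ms or more also required |
| QTcF (Table 10-3) | 501 ms or more | Change of 60 ms or more, but joined by OR |
| TEAE (10.2) | Not applicable | Not present before dosing, or worsened |

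The laboratory table differs from blood pressure, PR and TEAEs. It does not differ from the absolute limb of QTcF: a value of 501 ms or more before dosing and unchanged afterwards is also counted.

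**Step 2. Whether another summary fills the gap**

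Take a variable above the upper reference limit at Baseline. A subject who goes from Grade 1 to Grade 3 and a subject who is Grade 3 throughout both fall in the high-to-high cell of the shift table. Means and mean changes do not identify subjects.

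By-visit counts bound the answer but do not settle it. Let b be the number with Grade 3+ at Baseline, v the number at a later visit, and n the arm size, with all subjects measured both times. The number of new cases at that visit lies between max(0, v − b) and min(v, n − b).

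- b = 1, v = 1, n = 6: from max(0, 0) = 0 to min(1, 5) = 1. The same two counts fit one persisting case, or one resolved and one new case.
- b = 0, v = 1, n = 6: from 1 to min(1, 6) = 1. Here the case must be new.

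The ambiguity therefore arises when at least one subject is Grade 3+ at Baseline, or when the Baseline count is not displayed. Section 10.3 does not say whether it will be.

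**Step 3. Weight of one subject**

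Arm sizes come from Section 2.3: 15 in Dose Arms 1 and 2, and 6 to 12 in Dose Arms 3 to 5. The weight is 1/n if all subjects in the arm are measured at the visit.

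- n = 15: 1/15 = 6.7%
- n = 12: 1/12 = 8.3%
- n = 6: 1/6 = 16.7%

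**Step 4. The criteria themselves**

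The current text of Section 13.5 was not available for this check. Table 13-2 as set out in the Amendment 2 change list uses absolute limits for most variables. Two rows refer to baseline:

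- Creatinine: ">3.0xbaseline value OR >3.0xULN". The baseline limb is only one side of an OR, so the ULN limb still counts a pre-existing value.
- Hemoglobin increase: measured from baseline if baseline is above the ULN.

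That table has no platelet row and gives a single Grade 3+ threshold in each row.

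**The case against.** The strongest reply is that this is a prevalence table by visit and does not claim to be anything else. Section 10.3 does not call its counts treatment-emergent or drug-related; in the text at hand, that label is applied to vital signs and ECG. The phrase on visits does not exclude the pre-dose visit, whereas the shift tables are expressly limited to post-Baseline visits. A reader might infer that pre-existing abnormalities will be reported as on-drug findings. The document does not support that.

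Three further points stand:

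- A reader might infer that ECG as a whole is held to a treatment-emergent standard and laboratory data are not. The OR rule for QTcF shows otherwise.
- A reader might infer that every variable is judged without regard to Baseline, or that low platelet counts expected in ITP would fill the table. The logged Table 13-2 has baseline-referenced rows for creatinine and hemoglobin increase, and no platelet row.
- Individual tracing is possible. Grade 3+ results are listed separately, all laboratory values and changes are listed by subject, and Section 10.3.1 lists subjects meeting liver criteria, two of which refer to twice Baseline. In arms of 6 to 15 this can be done by hand.

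The primary safety variable is occurrence of TEAEs, which already has a worsening rule. What the reply does not answer is that the listings are the only place where Baseline and later Grade 3+ status are joined. The summary outputs do not do it.

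**Conclusion.** The point holds in a limited form. Section 10.3 summarizes Grade 3+ laboratory results without reference to Baseline, and the shift tables by reference range do not supply the missing link. Where a subject is Grade 3+ before dosing, the summaries cannot tell a persisting value from a new one. This is a weakness of presentation, not a contradiction or an error in the plan.

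One such subject weighs 6.7% at n = 15, 8.3% at n = 12 and 16.7% at n = 6. The SAP does not say how many subjects enter with Grade 3+ values, so no bias can be estimated, and it may be zero for many variables. The impact is limited to one supportive safety table.

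The conclusion assumes that the current Section 13.5 adds no Baseline condition beyond the two rows seen in the Amendment 2 change list. Nothing in the change lists suggests one. The change is worth making because it is cheap and because these arms have no other comparator.

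**What to change.** Keep the by-visit table in Section 10.3 as planned and add, for each laboratory variable and dose arm:

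- a row counting subjects with any Grade 3+ value after the first dose whose Baseline was below Grade 3;
- a separate row counting subjects who were Grade 3+ at Baseline.

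An equivalent choice is a shift table from Baseline with two categories, below Grade 3 and Grade 3+. Keep every Grade 3+ value in the listing. State also whether unscheduled values enter the new row, because Section 4.3 allows them in abnormality summaries without requiring it.

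A rule that also counts a rise to a higher grade than at Baseline is not advised. The logged criteria give one Grade 3+ threshold per row, so Grade 4 limits would have to be added first.

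The cost is one Baseline flag in the table program and a slightly longer table. No data are lost.
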